N-Acetylcysteine for Youth Cannabis Use Disorder

Study Protocol

NCT0305537

Most recent IRB-approved protocol dated April 14, 2022

PROTOCOL TITLE: N-Acetylcysteine for Youth Cannabis Use Disorder**PRINCIPAL INVESTIGATOR: [name].****OBJECTIVES/SPECIFIC AIMS**

Cannabis use is particularly prevalent and problematic among youth, who are more likely than adults to initiate cannabis use, develop cannabis use disorder (CUD), and suffer lasting adverse cannabis-related consequences. Despite the clear need for youth-targeted cannabis cessation treatments, established modalities offer limited efficacy, with very few youth achieving sustained cannabis abstinence.

Among the most promising emerging youth-targeted cannabis cessation treatments is the over-the-counter antioxidant medication *N*-acetylcysteine (NAC). Our team previously demonstrated superior NAC versus placebo (PBO) abstinence outcomes in youth with CUD who concurrently received the behavioral treatment contingency management (CM). In order to optimally translate NAC to real-world clinical practice, further work is now needed to evaluate if NAC is efficacious independent of CM.

We propose a 12-week randomized placebo-controlled trial of NAC for CUD in youth ($N=192$). Participants will be randomized to double-blind NAC or PBO, yielding two equally-allocated treatment groups. All participants will receive brief weekly cannabis cessation counseling and medication management. The primary efficacy outcome will be the proportion of negative urine cannabinoid tests during the 12-week active treatment, compared between groups. We will also assess cognitive task performance at baseline, during treatment, and after treatment, examining changes in performance among participants who achieve abstinence versus those that do not.

- *Specific Aim 1.* Compare the effect of NAC versus PBO, added to brief weekly cessation counseling and medication management, on cannabis cessation in youth with CUD.
 - Hypothesis 1: NAC participants will have a higher proportion of negative urine cannabinoid tests during treatment than PBO participants.
- *Specific Aim 2.* Examine the impact of cannabis cessation on cognitive task performance.
 - Hypothesis 3: Participants who achieve abstinence will demonstrate significant improvement in attention, processing speed, verbal declarative memory, and cognitive control, compared to those who continue to use cannabis.

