The primary study hypothesis was that participants randomized to NAC would have higher odds than those randomized to placebo to submit negative weekly urine cannabinoid tests (UCTs) during treatment. An intent-to-treat (ITT) approach including all randomized participants was used. In all analyses, participants lost to follow up or absent for visits were coded as having a positive UCT at every missed visit.

The proportion of negative UCTs in the NAC and PBO groups at each visit (ITT sample) is shown in the adjoining figure. Though there was no group difference in baseline years of cannabis use, this variable was an independent predictor of positive UCT during treatment ($p=0.007$) and was therefore covaried in the model. Participants randomized to NAC had more than double the odds of negative UCTs during treatment, compared with those randomized to PBO. In the adjusted model, the relationship between treatment and the odds of a negative UCT was $OR=2.4$ (95% CI: 1.1-5.4), $p=0.021$. Through the final treatment visit, 40.9% (190/464) of the UCTs among participants in the NAC group were negative, compared to 27.2%

(126/464) among those in the PBO group, per ITT analysis, assuming any missing urine was positive for cannabinoids. At the post-treatment follow-up visit (four weeks after medication discontinuation), 19.0% (11/58) of the UCTs among participants in the NAC group were negative, compared to 10.3% (6/58) among those in the PBO group. While still numerically favoring NAC, the overall treatment effect lost statistical significance at post-treatment follow-up ($OR=2.2$ [95% CI: 0.7-6.5], $p=0.155$), though the trial was not powered for this outcome.

Models were examined for the possibility of confounding and effect modification of age, weight, gender, and number of previous cannabis quit attempts. None of the variables tested were significant confounders or effect modifiers (all $p>0.60$).

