This study is powered on the hypothesis that there is a clinically significant difference in proportions of negative urine cannabinoid tests (UCTs) among participants receiving NAC versus PBO.

Our previous findings demonstrated proportions of negative UCTs of 41% with NAC+CM and 27% with PBO+CM, but given that CM is itself a powerful treatment, we anticipate more modest proportions without a CM platform (62). Based on our other prior work using pharmacotherapy without a CM platform, we anticipate the proportion of negative UCTs in the PBO group will be between 6% and 10% (61). Although we have no prior clinical results for estimates of the efficacy of NAC alone, we anticipate that it will be at least as efficacious as CM in the proportion of negative UCTs (~27%), resulting in an overall anticipated effect of NAC versus PBO of 25% vs. 10%. With 12 weekly observations taken on each participant, a conservatively estimated autocorrelation as high as $p=0.90$, and a first order autoregressive covariance pattern, we will have greater than 80% power with two-sided $\alpha=0.05$ to detect the stated difference of 15% in proportions of negative UCTs with 67 participants per treatment group ($n=134$ total). Based on performance of past studies, we anticipate a 30% attrition rate during the study treatment period. The inflated samples size of 96 randomized participants per group ($N=192$ total) will thus provide superior power to detect the stated difference in the main effect of NAC versus placebo in the presence of up to a 30% attrition rate.

Based on our previous research we anticipate approximately 25% percent of participants will have negative UCTs at cognitive task performance assessment visits (23). Similarly, our data indicate that negative UCTs were associated with increased verbal memory and psychomotor speed scores at both 4 and 8 weeks during a cannabis cessation trial using NAC + CM versus CM alone (Cohen's $d=0.90$ and $d=0.60$; respectively). The randomized sample size of $N=192$ will provide superior power (99% and 82%, respectively) with an adjusted $\alpha=0.01$, to detect similar effect sizes across cognitive outcome measures taken at mid-treatment, end-of-treatment, and post-treatment follow-up.

Statistical Analysis

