Categorical clinical and demographic variables will be assessed by chi-square tests of independence, while continuous variables will be assessed using Student's t -test. In addition to baseline group differences, preliminary analysis of baseline characteristics with cannabis use outcomes of interest will examine significant correlates of abstinence in the study population. Characteristics found to be significantly associated with cannabis use outcomes will be included as covariates in the initial stages of model development. The primary measure of interest will be the proportion of self-reported abstinence confirmed with negative weekly UCTs (< 50 ng/mL) during the 12 weeks of active treatment. The main effect of NAC on negative weekly UCTs will be assessed with a repeated measure logistic regression using a general estimating equations framework (GEE) (126). Models will be computed both unadjusted and adjusted for significant covariates and confounders found in the preliminary analysis. Working correlation structures will be independently compared using the quasi-likelihood under the independence model criterion statistic (127). All randomized participants will be included in the primary analysis (intent-to-treat; ITT) and participants will be deemed non-abstinent at any missed visit (drop-out/loss-to-follow up included). Model based means will be used to construct the pairwise comparisons of groups (NAC versus PBO). In addition to the longitudinal analysis of negative UCT rates during treatment, rates will be compared between treatment groups at each post-treatment follow-up visit using logistic regression models. Similarly, creatinine adjusted cannabinoid levels will be examined between groups over the course of the treatment and at the post-treatment follow-up visits using linear mixed effects models. We will also, in exploratory fashion, examine group differences in other cannabis-related outcomes (e.g., self-reported cannabis use [Timeline Follow-Back], craving [Marijuana Craving Questionnaire], withdrawal [Cannabis Withdrawal Scale], and associated problems [Marijuana Problem Scale]). In distinct models, the effect of co-occurring tobacco use disorder on cannabis cessation outcomes will be examined. The main effect of co-occurring tobacco use

disorder, as well as the interaction between tobacco use disorder and each treatment assignment (NAC and CM), will be added to the primary efficacy model.

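### The primary GEE is run unadjusted and adjusted with neither named as deciding, and the adjusted covariates are picked on the trial's own outcome data

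*Combined protocol and SAP*

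**What the plan says.** Section C3f (Statistical Analysis) fixes a good deal: a repeated-measures logistic GEE, all randomized participants, and a missing-visit rule under which "participants will be deemed non-abstinent at any missed visit". It then leaves the deciding fit open.

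- **Two versions.** "Models will be computed both unadjusted and adjusted for significant covariates and confounders found in the preliminary analysis". A primary efficacy model is mentioned later in the section, but it is tied to neither version.
- **Covariates.** "Characteristics found to be significantly associated with cannabis use outcomes will be included as covariates in the initial stages of model development". No p-value threshold, closed candidate list or final-model rule follows. C3c (Randomization) leaves gender, severity of the disorder and ADHD history to exploration during the efficacy analyses. Human Subjects section 4.4 (Quality Assurance) allows for adjustment if baseline characteristics differ between arms.
- **Strata.** C3c stratifies randomization by age (≤18, ≥19) and tobacco/nicotine use. C3f does not commit either factor to the primary model.
- **Working correlation.** "Working correlation structures will be independently compared using the quasi-likelihood under the independence model criterion statistic". No candidate structures are listed. The power section assumes "a first order autoregressive covariance pattern", but the analysis section does not adopt it.
- **Response.** Under Objectives/Specific Aims, "The primary efficacy outcome will be the proportion of negative urine cannabinoid tests during the 12-week active treatment". C3f instead describes self-reported abstinence confirmed by a negative urine test.

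**The concern.** Two eligible primary results exist, and the plan has no rule for the case where one is significant and the other is not. The content of the adjusted model is also unknown until outcome data have been examined. A reader of the final report could not tell whether the emphasized result was the one intended. At stake are modest inflation of the type I error if the more favorable result is emphasized, and an avoidable dispute over a borderline result.

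Leaving out the strata is a separate weakness. They were thought important enough to stratify on, and they are known at randomization, so they need no screening.

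**Working it through.** **1. The planned sample size reproduces.** Inputs from C3f (Power and Sample Size): 25% versus 10%, two-sided 0.05, 80% power, 12 visits, AR(1) at 0.90, 30% attrition.

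- Single-visit n per arm (unpooled) = (1.960 + 0.842)² × (0.25×0.75 + 0.10×0.90) / 0.15² = 7.849 × 0.2775 / 0.0225 = 96.80.
- Variance factor for a 12-visit mean = (1/144) Σ 0.9^|i−j| = 0.6864.
- 96.80 × 0.6864 = 66.4, so 67 per arm. Power at 67 is 80.3%.
- 67 / 0.70 = 95.7, so 96 per arm.

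The concern does not disturb the sample size.

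**2. Unadjusted versus screened, first simulation.** Assumptions: 192 participants; four strata; AR(1) 0.9 given covariates; nine candidates, of which age, tobacco, years of use and baseline level may be prognostic; screening at p<0.05 against outcome, pooled over arms; bias-corrected robust standard errors. Assumed log-odds for those four: none 0; mild −0.4/0.3/−0.3/−0.5; moderate −0.7/0.4/−0.5/−0.8; strong −1.0/0.6/−0.8/−1.2. There were 4,000 null runs per cell (10% in both arms; Monte Carlo SE 0.34 points) and 3,000 at 25% versus 10%. Each cell shows no attrition / 30% attrition coded non-abstinent, in percent.

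| Covariates | Disagree on significance, 25% v 10% | Null: either significant | Power, unadjusted | Power, screened | Power, fixed model |
|---|---|---|---|---|---|
| None | 0.8 / 1.1 | 5.4 / 5.2 | 91.7 / 86.5 | 91.8 / 85.9 | 90.9 / 85.3 |
| Mild | 3.6 / 3.8 | 5.8 / 5.5 | 90.9 / 86.4 | 91.4 / 86.8 | 91.7 / 87.1 |
| Moderate | 4.9 / 6.3 | 5.8 / 6.0 | 91.1 / 85.7 | 93.7 / 87.9 | 94.3 / 88.5 |
| Strong | 7.6 / 10.2 | 5.7 / 6.2 | 89.9 / 84.5 | 95.4 / 91.8 | 95.7 / 92.2 |

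Each single model rejected in 3.3 to 5.3% of null trials. Adding an imbalance rule gave disagreement of 1.5–2.0% (none), 3.9–6.4% (mild to moderate) and 7.6–10.1% (strong). The fixed model here held the strata, years of use and baseline level. With week terms, its null rejection rate was 3.9–5.5% (three cells, 1,500 runs each).

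**3. Second simulation, different assumptions.** It used 10 or 20 candidates, 0 to 4 of them prognostic, latent AR(1) 0.95, null rates of 10% or 17.5%, screening on outcome or imbalance, QIC choosing among three structures, and 4,000 runs per scenario. A pre-named model with a fixed correlation rejected in 4.8–5.5%. Either version significant: 6.1% (10 candidates, none prognostic), 7.5–7.6% (10, three prognostic) and 8.4% (20, four prognostic). QIC selection alone gave 5.2–5.4% unadjusted and 5.2–5.8% adjusted.

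**4. Working correlation.** With no week term, AR(1) weights are proportional to 1 for the first and last visit and (1−ρ) for each of the ten between. The two end weeks together carry 2 / [2 + 10(1−ρ)]: 66.7% at 0.90, 50% at 0.8 and 40% at 0.7, against 2/12 = 16.7% under independence.

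This moves the estimate only if the effect varies by week. As an assumed example, take no effect in week 1, half in week 2 and full effect d from week 3, with a 12-week mean of 15 points. Then d = 15 × 12 / 10.5 = 17.14. AR(1) at 0.9 without a week term targets 17.14 × (0.0333×0.5 + 9×0.0333 + 0.3333) = 17.14 × 0.65 = 11.1 points. Solving the expected estimating equations gives 11.9 with linear week and 17.6 with categorical week. Independence gives 15.0 in all three cases.

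**The case against.** The strongest reply is that each version is valid alone, that showing both is transparent, and that QIC is a stated criterion that does not look at treatment arm. Most of that stands. QIC selection leaves type I error near nominal, the 67% weight needs ρ at the top of the planned range, and the delayed effect in step 4 comes from no section of the protocol. What does not stand is that showing both settles the matter: it does not say which result decides when they differ.

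The size also depends on assumed prognostic strength. C1a reports that in the prior trial age, weight, gender and quit attempts were neither significant confounders nor effect modifiers (all p>0.60). That is not a test of prognosis, but it gives no support to the stronger age effects assumed. The disagreement rates also include ordinary power differences between two valid models, not only error.

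Two stronger readings are tempting:

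- **Data-driven choice inflated the prior trial's result.** The C1a counts give a crude odds ratio of (190×338)/(274×126) = 1.86, against a reported adjusted 2.4. The protocol does not attribute this gap to covariate selection. Conditional and crude odds ratios differ without any selection, and the correlation structure or other model terms may contribute.
- **The plan lets the sponsor claim whichever result is significant.** No section says so. The 5 to 8% figure applies only under that unstated rule.

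Independence is sometimes defended on the ground that every participant has 12 values. The plan does not guarantee this: C3b (Retention Strategies) and C3d (Remote Visits) allow an attended remote visit without a urine sample, and no rule codes it.

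**Conclusion.** The point holds as a should-fix. The deciding version is unnamed, its covariates are selected on trial outcomes, and the strata are not committed to it. The harm is modest: about 5 to 8% type I error if either result could be claimed, and disagreement at the planned effect in about 1% of trials (nothing prognostic) to about 4–10% (mild to strong). These ranges rest on assumed covariate strengths and candidate numbers, so they are not estimates for this trial. The working correlation is secondary: its candidate list is missing and it can change the weighting of weeks, but it has little effect on type I error.

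**What to change.** Before unblinding, name one primary model in C3f:

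- **Model.** Logistic GEE on the weekly response with treatment, categorical week, age stratum, tobacco/nicotine stratum and log baseline creatinine-normalized cannabinoid level. Take the week 0 value, else screening, else the overall mean regardless of arm. Years of cannabis use is optional; its support is the one prior trial in C1a.
- **Correlation and standard error.** One fixed structure with a robust standard error. Either independence or the AR(1) of the power section is acceptable; label the other supportive.
- **Screening.** Remove significance and imbalance as routes into the primary model, and label the unadjusted fit supportive.
- **Reporting.** Give the standardized difference in proportions with its confidence interval beside the odds ratio.
- **Response.** Choose one of the two definitions, and code an attended visit without a urine result as non-abstinent, like a missed visit, so that everyone has 12 values.
- **Tidy-up.** Delete the contingency-management interaction in C3f, since this trial has no such assignment.

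No new data are needed. Strata are known at randomization, and the Study Timetable already schedules the assay at screening and week 0.

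The costs are as follows. Power falls by 0.8–1.2 points against the unadjusted model if nothing is prognostic, and rises by 0.7–3.2 with mild to moderate covariates and 5.8–7.7 with strong ones. Fixing independence costs 1.1–2.9 points if AR(1) 0.9 holds with a constant effect; by formula, 67 per arm gives 80.3% against 83.4%. These power runs included years of use, so they are a guide. No section shows that baseline level predicts outcome; it is proposed as the baseline of the outcome measure. The adjusted odds ratio is conditional (simulated medians 3.1–4.5 where the marginal value is 3.0), which is why the standardized difference is needed.

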During the 12 weeks of treatment, participants will be asked to record and upload twice-daily videos of medication-taking at home or in a private location of their choosing. These videos will be taken remotely and submitted via REDCap surveys to confirm medication adherence. Participants may use their personal mobile phones for video submission. If they do not have a smartphone, one will be loaned to them during the first week of study. Video submissions may only be completed on a smartphone (cannot be completed on a computer). A survey link will be sent to the participant via text message. Video capture will occur as part of the REDCap survey. Videos are automatically stored on Android smartphones, and participants will be informed of that so they can delete the files, if necessary. Participants using iPhones (and using loaner iPhones from our group) will not have stored videos on their phone and nothing will need to be deleted.

Laboratory Tests

Urine pregnancy tests will be conducted with female participants. Weekly urine samples will be tested both qualitatively via dipstick as well as analyzed by the laboratory for quantitative urine cannabinoid level (with cutoff of <50 ng/mL signifying a cannabinoid-negative urine). Quantitative urine creatinine will also be obtained, to allow for evaluation of creatinine-normalized urine cannabinoid levels for quantitative comparisons (123,124).

Cognitive Task Performance Assessments

CNS Vital Signs, a computer-administered battery of performance tests, assessing subtle changes in mental acuity, learning and memory, psychomotor speed, complex attention, impulsivity, planning and sequencing, and other aspects of performance, will be administered at baseline, during treatment, at treatment conclusion, and at post-treatment follow-up (125). A training/practice session will be conducted during screening. The

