Pittsburgh Sleep Quality Index	X ^{!△}	X								X					X	X	X
Columbia Suicide Severity Rating Scale	X [!]	X\$								X					X	X	X
Cognitive Task Performance Testing	X#!	X								X					X		X
Substance Self-Report																	
Cannabis and Other Substance Use History	X! ^{!△}																
Cannabis Quantification	X																
TLFB/Substance Use Daily Reports	X%! ^{!△}	X\$	X	X	X	X	X	X	X	X	X	X	X	X	X	X	X
Cannabis Withdrawal Scale	X	X	X	X	X	X	X	X	X	X	X	X	X	X	X	X	X
Marijuana Craving Questionnaire	X	X	X	X	X	X	X	X	X	X	X	X	X	X	X	X	X
Marijuana Problem Scale	X								X						X	X	X
Obsessive Compulsive Drug Use Scale	X								X						X	X	X
Modified Fagerström Tolerance Questionnaire (mFTQ) and/or Penn State Electronic Cigarette Dependence Index	X ^{!△}																
Motivation and Confidence to Quit	X	X															
Lab Samples/Testing																	
Urine drug test (dipstick)	X ^{!△}	X [^]	X	X	X	X	X	X	X	X	X	X	X	X	X	X	X
Urine Cannabinoids & Creatinine assay	X	X	X	X	X	X	X	X	X	X	X	X	X	X	X	X	X
Urine Pregnancy Test [‡]	X [△]	X\$	X*	X*	X*	X*	X*	X*	X	X*	X*	X*	X*	X*	X*	X	
Psychosocial Procedures																	
Medication Adherence Assessment (Pill Count, Daily Reports, and REDCap Video Review)			X	X	X	X	X	X	X	X	X	X	X	X	X	X	
Cessation Counseling/ Medication Management		X	X	X	X	X	X	X	X	X	X	X	X	X	X		
Medication Dispensation		X	X	X	X	X	X	X	X	X	X	X	X	X	X		
Estimated Visit Length (hours) →	2-3	1.5	.75	.75	.75	.75	.75	.75	1.5	.75	.75	.75	.75	.75	1.5	1	1.5

SC=Screening/Assessment, FU=Follow-Up, ET=Early Termination

ø the week 0 visit is the Randomization Visit, ♀ females only, * PRN for safety/precautionary measure, ^ Urine drug test should be performed at screening/baseline and again before randomization to ensure eligibility, \$ should be completed prior to randomization to ensure eligibility. & If week 6 visit is missed, assessments that are only completed at that visit should be performed at the next attended visit, as long as the window for the end-of-treatment (week 12) visit has not yet opened. % These assessments may be performed at the randomization (week 0) visit, as long as they occur prior to randomization to ensure eligibility. # Training/practice cognitive task performance session. ; ^ data sharing of completed protocol procedures from PRO#80921 as a result of screen failure, > at ET if completed during treatment phase of protocol; ^ data sharing of completed protocol procedures from PRO#94743

C3f. Statistical Methods

Power and Sample Size

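### The mixed models for creatinine-adjusted cannabinoid level name no pre-treatment level, randomisation strata or scale, which may cost material precision during treatment

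*Combined protocol and SAP*

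**What the plan says.** The specification of this outcome is one sentence in C3f, Statistical Analysis: "creatinine adjusted cannabinoid levels will be examined between groups over the course of the treatment and at the post-treatment follow-up visits using linear mixed effects" regression. It gives no baseline term, change score, transformation or covariance structure, and it does not say whether week 0 belongs to the response vector.

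The data for adjustment are collected. C3e, Laboratory Tests, gives the purpose of the creatinine measurement: "to allow for evaluation of creatinine-normalized urine cannabinoid levels for quantitative comparisons". In the Study Timetable the row "Urine Cannabinoids & Creatinine assay" is marked at screening, at week 0 and at every later visit. Week 0 is the randomisation visit and the first visit at which medication is dispensed.

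C3c, Randomization, stratifies by age (18 or under versus 19 or over) and by current tobacco/nicotine use. The quantitative analysis names neither stratum.

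C3f also has a general covariate rule. Baseline characteristics that prove significantly related to cannabis use outcomes become covariates early in model building, and models are run both with and without adjustment. Neither version is called the lead.

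**The concern.** Everyone must have a positive urine cannabinoid test at screening. The binary baseline therefore carries no information, while the quantitative level still varies and is the natural prognostic variable for later levels. If it is left to a significance screen, the reported precision and the choice of headline model depend on the data.

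At stake is the only continuous between-group cannabis outcome that the section lists before it turns to exploratory outcomes. It can show reduced use that the 50 ng/mL cut-off misses.

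Missing data add a second reason. Counting a missed visit as non-abstinent supplies no numeric level, so this outcome relies on the ignorable-attrition assumption under Missing Data and Attrition. That assumption works through covariates and earlier values of the outcome, and the pre-treatment level is the first of these. The plan expects 30% attrition.

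**Working it through.** **1. The plan's own figure.** Power and Sample Size states a sample size only for the binary outcome: "we will have greater than 80% power with two-sided" alpha 0.05, "to detect the stated difference of 15% in proportions of negative UCTs", for 25% versus 10%. "With 12 weekly observations taken on each participant" and "a conservatively estimated autocorrelation as high as" 0.90 (AR(1)) are the other inputs.
- Single observation, unpooled variance: n = (1.960 + 0.842)² × (0.25×0.75 + 0.10×0.90) / 0.15² = 96.8 per group.
- Variance factor for the mean of 12 AR(1) observations: (1/144) Σ 0.9^|i−j| = 0.686.
- 96.8 × 0.686 = 66.4, so 67 per group. 67 / 0.70 = 95.7, so 96.

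The stated 67 and 96 reproduce. No SD, correlation, target effect or power is given for the quantitative level, so everything below is conditional on assumed correlations.

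**2. Formula for the gain.** Take unit variance at each visit, one pre-treatment value and the mean of 12 weekly values.
- V = variance of the 12-week mean.
- c = its covariance with the pre-treatment value.
- Share of variance removed by adjustment = c² / V.
- AR(1): V = (1/144) Σ ρ^|i−j| and c = (1/12) Σ ρ^k for k = 1 to 12.
- Compound symmetry: V = (1 + 11ρ)/12 and c = ρ.

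**3. Results for the 12-week mean.** The last column is the power after adjustment if the unadjusted power were 80%.

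| Structure (assumed) | V | c | Variance removed | Power, from 80% |
|---|---|---|---|---|
| AR(1) 0.5 | 0.222 | 0.083 | 3% | 81% |
| AR(1) 0.7 | 0.366 | 0.192 | 10% | 84% |
| AR(1) 0.90 | 0.686 | 0.538 | 42% | 96% |
| Compound symmetry 0.5 | 0.542 | 0.500 | 46% | 97% |

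The 0.90 is the plan's value for the binary test and is borrowed here. The power column is Φ(2.802/√(1 − c²/V) − 1.960).

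**4. Follow-up visits.** Under AR(1) 0.90 the correlation with the pre-treatment value is 0.9^16 = 0.185 at week 16 and 0.9^26 = 0.065 at week 26. The variance removed is the square of this: 3.4% and 0.4%.

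**5. Strata and scale.** The documents give no figures from which to size either one. They are points of specification only.

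**The case against.** The strongest reply is that the section is silent and has not decided against adjustment. The covariate rule speaks of cannabis use outcomes in the plural. Section 4.4 (Quality Assurance) promises an initial look at distributions and baseline comparability in case adjustment is needed. If the pre-treatment level were screened and its correlation with outcome were 0.5 or more, a 5% test would select it with probability above 99.99% at n=134 or 192 (Fisher z). At 0.3 the probability would be 94% to 99%. If week 0 were modelled as a response with a common mean, much of the gain would also return. And the exploratory aim speaks of a reduction in quantitative tests, which implies a starting value.

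Much of this stands. A reader might infer that the plan chose an unadjusted raw-scale analysis and so wastes much of the power of its main quantitative outcome. The documents do not support that. They state no scale, do not exclude the baseline, do not call this the main quantitative outcome and claim no power for it. A single-visit calculation (1 − ρ², or 25% to 49% of variance at ρ = 0.5 to 0.7) is also not the planned analysis, which runs over 12 weekly visits.

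The reply does not close the gap. The screen is described as a search for correlates of abstinence, and it neither names nor guarantees the pre-treatment level. An unadjusted model remains with no lead chosen, and the text does not say that week 0 is a response. The tobacco models in C3f extend the primary efficacy model and concern tobacco use disorder, so they do not supply the stratum here.

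**Conclusion.** The point holds as a gap in prespecification. The pre-treatment level, the strata and the scale are not fixed for this outcome, although the level and the strata are available for every properly randomised participant. The possible loss of precision during treatment runs from trivial (about 3%) to substantial (42% to 46%), depending on a correlation structure that the documents do not give. Under AR(1) 0.90 it is close to nil at weeks 16 and 26. No stated figure is wrong, and the primary binary test, its alpha and N=192 are untouched. The change is worth making because it is nearly free and removes a data-driven choice of model. A claim of large lost power would go beyond the evidence.

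**What to change.** In C3f, name one lead model for this outcome:
- a linear mixed model on log(cannabinoid/creatinine);
- the pre-treatment log value (week 0, or screening if week 0 is missing), the age stratum and the tobacco/nicotine stratum as fixed covariates, whatever their significance;
- NAC/PBO geometric mean ratios with confidence intervals as the reported result.

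The unadjusted model can stay as supportive.

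The cost is wording only, since all the data are already scheduled. There are two downsides. One rule for values below the assay limit must be fixed before unblinding; this matters because the plan anticipates 10% to 25% of tests under 50 ng/mL, and some of those may lie near the limit. The estimand also becomes a ratio of geometric means, which is partly a matter of preference. If the team keeps the raw scale, it should still adjust for the pre-treatment level and the strata.
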